13.2 Sample Size

Inclusion Criteria are men with IIEF scores >11 which includes men with mild (IIEF 16-21) and mild/moderate (12-16) Erectile dysfunction. Minimal clinically important differences (MCID) for these groups are an increase of 2 for mild and 5 for moderate ED. Previous studies on the effect of placebo show about a 15% improvement in men with mild to moderate ED. Therefore, 15% of the placebo group is expected to meet MCID. Results from the PRP safety study by Matz et al. 2018, which showed a mean improvement in IIEF of 4.14 points in seven patients with ED after PRP. In the interventional group, we expect 50% to meet MCID. At 80% power, we will therefore need 30 patients in each group to detect a difference of 35% between treatment and placebo arms.

$$\text{Sample size} = \frac{2(Z_{\alpha/2} + Z_{\beta})^2 P(1 - P)}{(p_1 - p_2)^2}$$

$$28.08 = (2*(1.96+0.84)^2 * (0.25*(1-0.25)) / (0.35^2)$$

Assuming attrition of approximately 20%, an additional 6 participant slots will be added to each group for a total sample size of 80 subjects.

14. Risks to Subjects

We anticipate there to be few adverse events related to the study. Based on the four published studies and abstracts, including 75 men, only minor adverse events were reported (Bruising 1, Mild Pain 4). No serious adverse events were observed [23-26] (Table 2). After literature review, we believe this product to be of non-significant risk to patients (NSR) and for investigational use in a clinical study protocol.

Based on published studies, we will record anticipated adverse events to patients include: local injection site reaction, penile pain and penile bruising. Additionally, we anticipate

patients may experience, penile swelling, allergic reaction, local infection (though none reported in previous studies) and will record them at every visit systematically.

15. Potential Benefits to Subjects

The potential benefits for men randomized to the treatment arm will include improvement in erectile function and sexual performance.

16. Privacy & Confidentiality

Each subject's protected health information will remain strictly confidential and shall be excluded from the database. Patients deemed eligible to participate in the study following evaluation of inclusion/exclusion criteria will be assigned a unique study participant identifier number (ex.: 01-PRP01-001). The first two characters indicate the enrolling site, next 5 characters describe the study and phase, and final 3 characters are the unique identification number assigned to subjects in sequential order. Only each participant's initials, assigned study participant identifier number, and date of birth may be documented in the database. The Investigator will retain a cross-referencing record of each subject's name and assigned identifier number. All study data and results will be stored in the electronic database. Each study subject will give explicit consent for representatives of the IRB/IEC and regulatory authorities to inspect and verify each subject's medical records and collected information. In turn, each study subject will be assured that all their personal information will be maintained in the strictest of confidence, and in compliance with HIPAA, and all other federal and local laws regulating privacy and data protection.

17. Ethical Considerations

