| STUDY DESIGN | Randomized, Double Blind, Placebo Controlled, Pilot Trial |
| ROUTE OF ADMINISTRATION | Intracavernosal Injection |
| SUBJECT POPULATION | 80 male subjects between the age of 30-75 with erectile dysfunction of organic origin |
| STUDY OBJECTIVES | 
Primary: To investigate and compare the treatment efficacy of PRP vs placebo treatment in men with mild-moderate ED, as measured by IIEF.
 
Secondary: To study incidence of adverse events and safety of PRP injection treatment in men with mild-moderate ED, as measured by IIEF.
 |
| INVESTIGATION PLAN | 
80 men with Erectile Dysfunction (ED) of organic origin, that meet all of the inclusion and none of the exclusion criteria, will be randomized to receive, intracavernosal injection of either PRP or placebo in a 1:1 double-blinded fashion:
 
Group A (40 subjects): Autologous PRP All subjects in this group will receive 2 sessions of autologous PRP with 30 ± 7 day treatment interval. 5mL of PRP will be injected at each session.
 
Group B (40 subjects): Placebo (Normal Saline) All subjects in this group will receive 2 sessions of normal saline with 30 ± 7 day treatment interval. 5mL of normal saline will be injected at each session.
 
 - Patients will be followed for outcome assessments at 1, 3, and 6 months post final injection. |
| DURATION OF STUDY | 9 months (1 month screening, 2 therapy sessions 1 month apart, 6 months follow-up) |
| DEFINITION OF ENDPOINTS | 
Primary Endpoint (Efficacy)
 
 - The percentage of subjects in each group who attain MCID in IIEF-EF domain from baseline to 4 weeks after final treatment. 
Secondary Endpoints (Efficacy)
 
 - The percentage of subjects in each group who attain MCID in IIEF-EF domain from baseline to 12 & 24 weeks after final treatment. - The difference between groups in change of IIEF-EF score from baseline to 4, 12, & 24 weeks after final treatment. - Differences in Doppler ultrasound parameters (PSV and EDV) from baseline to 24 weeks after final treatment. 
Secondary Endpoints (Safety)
 
 - Incidence of adverse events in all patients during the study period. |

| | |
|--------------------|--|

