5.1 Additional Study Sites

No additional study sites.

6. Study Population

80 males with ED of organic origin. All patients will be regular PDE5i users/responders. After a 1-month wash-out period for PDE5i, men with ED will be evaluated by IIEF-EF domain and eligible patients will be randomized to one of 2 treatment groups with an equal allocation ratio (1:1). Participants who do not adhere to the 1-month wash-out period, or do not meet the IIEF-EF domain score will be considered a screen failure and will not receive the study therapy.

6.1 Inclusion criteria: In order to participate in this study, a patient must:

- 1) Be Male
- 2) Be 30 to 75 years of age (inclusive).

- 3) Be able to provide written informed consent.
- 4) Have a diagnosis of ED due to organic origin for at least 6 months prior to consent.
- 5) Sexually active in a stable, heterosexual relationship of more than three months duration.
- 6) IIEF-EF score 11-25 at screening (even if taking a single PDE5).
- 7) Agree to attempt sexual intercourse at least 4 times per month for the duration of the study without being under the influence of alcohol or recreational drugs.
- 8) Agree to comply with all study related tests/procedures.

6.2 Exclusion criteria: In order to participate in this study, a patient must not:

- 1) Previous penile surgery of any kind (except circumcision and condyloma removal), such as penile lengthening, penile cancer surgery, penile plication, grafting.
- 2) Previous history of priapism or penile fracture
- 3) Abnormal morning serum testosterone level defined as a value lower than 300 ng/dL ($\pm 5\%$) (indicative of untreated hypogonadism), or greater than 1197 ng/dL ($\pm 5\%$).
- 4) Current or previous hormone usage, other than prescribed testosterone, clomiphene or thyroid medication. (Subjects with prior or current use of hormonal treatment for prostate cancer are also excluded.
- 5) Psychogenic ED as determined by study investigator.
- 6) Anatomical (Peyronie's Disease or penile curvature that negatively influences sexual activity) or neurological abnormalities in the treatment area.
- 7) Patients using ICI for management of ED
- 8) Patients with generalized polyneuropathy, or neurological conditions irrespective of cause, such as severe diabetes, multiple sclerosis or Parkinson's disease.

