7.4 Withdrawal Criteria

All subjects who either screen fails, is withdrawn from the study, or has completed all visits should be de-enrolled from the research database within 2 business days, in accordance with university policies (or respective institutional policy).

Subjects may be withdrawn from the study for any of the following reasons:

- a) A subject does not meet the eligibility criteria (the subject will be considered a screen failure).
- b) A subject withdraws consent
- c) A subject expires during protocol participation from causes other than the study treatment (not due to adverse events)
- d) At the discretion of the principal investigator for issues of non-compliance, or other behavioral factors.

8. Procedures Involved

72 men with Erectile Dysfunction (ED) of organic origin, that meet all of the inclusion and none of the exclusion criteria, will be randomized to receive either PRP, or placebo in a 1:1 double-blinded fashion.

- a) Group A (40 subjects): Autologous PRP injection. All subjects in this group will receive 2 sessions of autologous PRP penile injection with 30 ± 7 day treatment interval. 10mL of PRP will be injected at each session.
- b) Group B (40 subjects): Placebo (Normal Saline). All subjects in this group will receive 2 sessions of normal saline penile injection with 30 ± 7 day treatment interval. 10mL of normal saline will be injected at each session.

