13.1 Data Analysis Plan

Analysis plan: Continuous data will be analyzed using ANOVA with repeated measures, or student's T-Test (where applicable) in order to compare differences between the treatment and control groups. For categorical data, Fisher's Exact test to determine differences between groups. Statistical significance will be evaluated using $\alpha=0.05$.

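### Section 13.2 does not support its total of 80: the printed P is wrong, 30 + 6 per group makes 72, Section 8 gives both 72 and 40 + 40, and the planned Fisher's exact test has 77.7% power at 30 per arm

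*Combined protocol and SAP*

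**What the plan says.** Section 13.2 assumes that 15% of the placebo group and 50% of the PRP group reach the MCID. It prints the calculation "28.08 = (2*(1.96+0.84)^2 * (0.25*(1-0.25)) / (0.35^2" and concludes: "At 80% power, we will therefore need 30 patients in each group to detect a difference of 35% between treatment and placebo arms". For attrition of about 20%, it states that "an additional 6 participant slots will be added to each group for a total sample size of 80 subjects".

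The number to be randomised appears in three other places:

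- Synopsis, Investigation Plan: "80 men with Erectile Dysfunction (ED) of organic origin", in two groups of 40.
- Section 6: "80 males with ED of organic origin".
- Section 8: "72 men with Erectile Dysfunction (ED) of organic origin", followed directly by "Group A (40 subjects): Autologous PRP injection" and a Group B that is also of 40.

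The primary endpoint (Section 4.1) is a proportion in each group. For categorical data Section 13.1 names Fisher's "Exact test to determine differences between groups", with alpha 0.05.

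**The concern.** A reader who follows Section 13.2 line by line does not arrive at its total. The equation does not equal the figure beside it, and 30 plus 6 in each of two groups is not 80. The total that does follow, 72, is the one that opens Section 8, so two sample sizes stand in the protocol and 80 has no valid derivation.

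The 80% power also belongs to a different test from the one planned. Fisher's exact test is conservative at this size and needs more men than the uncorrected normal approximation suggests. What is at stake is the number randomised and whether the claimed power for the primary comparison survives the plan's own attrition.

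**Working it through.** **Inputs.** From Section 13.2: placebo rate 0.15, PRP rate 0.50, z values 1.96 and 0.84, 30 per group, 6 added per group, attrition about 20%. From Section 13.1: Fisher's exact test, alpha 0.05. From Section 9.3: 1:1 allocation. The 1.96 in the formula makes the calculation two-sided.

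**Step 1: the printed equation.** The formula is n = 2(z_α/2 + z_β)² P(1 − P) / (p1 − p2)².

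- With the printed P: 2 × 2.80² × 0.25 × 0.75 / 0.35² = 24.00.
- With the mean of the two rates, P = (0.15 + 0.50) / 2 = 0.325: 2 × 2.80² × 0.325 × 0.675 / 0.35² = 28.08.

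The stated 28.08 is therefore right for the stated rates, and the stated 30 per group is 28.08 rounded up generously. Only the printed P is wrong.

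**Step 2: the total.**

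- As the sentence is written: 2 × (30 + 6) = 72. The 6 extra places cover a loss of 6/36 = 16.7%, not 20%.
- With the usual inflation: 30 / 0.80 = 37.5, so 38 per group and 76 in total.
- To arrive at 80 by that inflation, the evaluable number must be 40 × 0.80 = 32 per group, a figure Section 13.2 does not give.

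**Step 3: Section 8.** It opens with 72 and lists 40 + 40 = 80.

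**Step 4: power of the planned test.** All pairs of binomial outcomes for 50% versus 15% were enumerated, counting those with a two-sided Fisher p ≤ 0.05.

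| Evaluable per arm | Fisher power |
|---|---|
| 28 | 75.2% |
| 29 | 75.7% |
| 30 | 77.7% |
| 31 | 79.7% |
| 32 | 81.5% |
| 40 | 89.8% |

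With equal arms, 32 is the first size to reach 80%, and power stays above 81.5% at every size from 33 to 40. For comparison, the normal approximation gives 84.3% at 30 per arm.

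**Step 5: power after 20% attrition**, taking men lost as absent from the analysis.

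| Randomised | Evaluable | Equal arms | Uneven arms (PRP/placebo) |
|---|---|---|---|
| 72 | 72 × 0.8 = 57.6 | 75.2% (28), 75.7% (29) | 79.8% (28/29), 77.4% (29/28), 80.0% (28/30), 81.0% (30/28) |
| 80 | 80 × 0.8 = 64 | 81.5% (32) | 83.6% (31/33), 84.5% (33/31), 83.9% (30/34), 83.3% (34/30) |

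**Side calculation.** The placebo rates here are assumptions of this review, not figures from the plan. With PRP held at 50% and 32 per arm, Fisher power is 64.4%, 46.0% and 29.8% at placebo rates of 20%, 25% and 30%.

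**The case against.** The strongest reply is that 80 is plainly the intended number. It stands in the synopsis, in Section 6, at the end of Section 13.2 and in the group sizes of Section 8; only one phrase says 72. On that reading the 0.25 is a misprint with no consequence, the per-group figure of about 30 does reproduce, and the Fisher shortfall disappears, because 80 randomised with 20% lost leaves 32 per arm and 81.5%. The trial is also described as a Phase I pilot.

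Most of this is fair. The 0.25 did not feed into any figure the trial uses, and the shortfall of 2.3 points at 30 per arm matters mainly if 72 is the operative total. But the 72 is not a stray digit: it is exactly what the arithmetic in Section 13.2 yields. And, pilot or not, the section claims 80% power for the primary comparison.

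Two technical limits also stand. Fisher power is uneven in n because the test is discrete: 29/30 gives 81.6%, more than 30/30. The threshold of 32 therefore holds for equal arms only. The attrition figures further assume that lost men drop out of the analysis; Section 13.1 defines no analysis set, and counting them as non-responders would change both denominators and rates.

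Finally, 32 evaluable per arm is not in the protocol. The sponsor may have reached 80 by another route and, if so, should print that route.

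**Conclusion.** The point holds and must be fixed. The printed equation is false (24.00 against 28.08). The stated steps lead to 72 and not 80. Section 8 contradicts itself. The 80% power at 30 per group is not that of the planned test, which has 77.7%. The figure of 28.08, and hence about 30 per group, is sound under the plan's own formula.

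The conflict over the total has the greatest effect. Under 20% attrition, 80 randomised gives 81.5% in equal arms and at least 83.3% in the uneven splits examined. With 72 the range is 75.2% to 81.0%, so the stated power is not reliably met. These results rest on rates of 50% and 15%, a two-sided test at 0.05, and an analysis of evaluable men only. The sensitivity to the placebo rate is a secondary remark, and the verdict does not depend on it.

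**What to change.** 1. In the Section 13.2 equation, print P = 0.325.
2. In Section 8, change 72 men to 80 men, to agree with the 40 per group listed beneath it, the synopsis and Section 6.
3. In Section 13.2, replace the 30 per group and the 6 added places with a derivation that leads to 80. One that works: 32 evaluable men per arm give 81.5% power with a two-sided Fisher's exact test at alpha 0.05 for 50% versus 15%; allowing for 20% attrition, 32 / 0.80 = 40 per arm, 80 in total. If the sponsor had a different derivation, that should be printed instead, with power given for the planned test.
4. Less pressing: say whether the 15% placebo improvement is a share of men or a mean score change, cite its source, and report power at placebo rates of 20%, 25% and 30% with PRP held at 50%.

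The cost is wording only: no men beyond the 80 already planned, and no change of test or alpha.

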17.1 Regulatory Authority Approval

This study will be conducted in accordance with Good Clinical Practice (GCP) requirements described in the current revision of International Conference on Harmonization of Technical Requirements of Pharmaceuticals for Human Use (ICH) Guidelines and all applicable regulations, including current United States Code of Federal Regulations (CFR), Title 21, Parts 50, 54, 56, and Title 45, Part 164. Compliance with these regulations and guidelines also constitutes compliance with the ethical principles described in the current revision of the Declaration of Helsinki. This study will also be carried out in accordance with local legal requirements.

According to FDA guidance issued to institutional review boards and investigators, we will use PRP for ED (an indication not approved on the labeling) while simultaneously "bearing the responsibility to be well informed about the product, base its use on firm scientific rationale and on sound medical evidence, and to maintain records of the product's use and effects."

We believe that according FDA regulation, the clinical investigation of PRP for ED does not require submission of an IND / IDE since all six of the following conditions are met:

- i. it is not intended to be reported to FDA in support of a new indication for use or to support any other significant change in the labeling for the drug;
- ii. it is not intended to support a significant change in the advertising for the product;

- iii. it does not involve a route of administration or dosage level, use in a subject population, or other factor that significantly increases the risks (or decreases the acceptability of the risks) associated with the use of the drug product;
- iv. it is conducted in compliance with the requirements for IRB review and informed consent [21 CFR parts 56 and 50, respectively];
- v. it is conducted in compliance with the requirements concerning the promotion and sale of drugs [21 CFR 312.7]; and
- vi. it does not intend to invoke 21 CFR 50.24.

17.2 Ethics Approval

The investigators agree to conduct the study in compliance with the protocol, current good clinical practices, and all applicable (local, FDA) regulatory guidelines and standard of ethics.

It is the Investigator's responsibility to ensure that, prior to initiating this study, this protocol is reviewed and approved by the appropriate local and/or external IRB. The composition and conduct of this committee must conform to the United States CFR. The IRB/IEC must also review and approve the site's informed consent form (ICF), other written information provided to the subject.

If it is necessary to amend the protocol or the ICF during the study, the Sponsor-Investigator will be responsible for ensuring that the IRB/IEC reviews and approves these amended documents. An IRB/IEC approval of the amended protocol and/or ICF must be obtained in writing before implementation of the amended procedures and before new subjects are consented to participate in the study using the amended version of the ICF.

